3 SELECTION OF PATIENTS

3.1 Inclusion Criteria

- 3.1.1 Voluntary written informed consent before performance of any study-related procedure not part of normal medical care, with the understanding that consent may be withdrawn by the subject at any time without prejudice to future medical care.
- 3.1.2 ≥ 60 years old.
- 3.1.3 Previously untreated classical Hodgkin lymphoma (i.e., nodular sclerosis, mixed cellularity, lymphocyte depleted, lymphocyte-rich, and NOS). Nodular lymphocyte predominant Hodgkin lymphoma is not eligible.
- 3.1.4 Stage II, III, and IV disease by Ann Arbor classification.
- 3.1.5 ECOG performance status score of 0, 1, or 2.
- 3.1.6 Patients must have bi-dimensional measurable disease (as defined in section 6.1) within 60 days prior to starting treatment (at least 1.5 cm). Patients with non-measurable disease (defined in Section 6.1) in addition to measurable disease must have been assessed within 60 days prior to starting treatment.
- 3.1.7 Patients must have a bone marrow biopsy (bilateral preferred, unilateral acceptable) within 90 days prior to starting treatment.
- 3.1.8 Patients must have a MUGA or echocardiogram within 90 days prior to starting treatment and the ejection fraction must be $\geq 45\%$.
- 3.1.9 Adequate organ function including an ANC $> 1000/\text{mm}^3$, platelet count $> 75,000/\text{mm}^3$, creatinine < 2.5 mg/dl, and bilirubin < 3.0 mg/dl. Patients with documented marrow involvement by lymphoma at the time of registration are not required to meet the above hematologic parameters.
- 3.1.10 Patients must not have received prior chemotherapy or radiation therapy for the treatment of Hodgkin lymphoma.
- 3.1.11 Both females and males who have partners of childbearing potential must agree to use an effective contraceptive method during the study and for 30 days following the last dose of study drug.
- 3.1.12 Patients must sign the informed consent form before registration.

3.2 Inclusion of Women and Minorities.

- 3.2.1** Both men and women and members of all races and ethnic groups are eligible for this trial.

3.3 Exclusion criteria.

- 3.3.1** Previous treatment with SGN-35 or any other prior anti-CD30-based antibody therapy.
- 3.3.2** No currently active other (second) malignancy, other than non-melanoma skin cancers. Patients are not considered to have a “currently active” malignancy if they have completed anti-cancer therapy and are considered by their physicians to be at less than 30% risk of relapse.

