- 3.3.3** Known cerebral/meningeal disease.
- 3.3.4** Any active systemic viral, bacterial, or fungal infection requiring IV treatment with antimicrobial therapy within 1 week prior to first dose.
- 3.3.5** Patients with known HBsAg positive HBV infection. Patients with prior history of Hepatitis B infection, but immune, with only IgG Hepatitis core antibody + (HBcAb +) must receive anti-viral prophylaxis (e.g., lamivudine 100mg po daily) for at least 1 week prior to cycle 1 and throughout induction and continuation therapy and for at least 6 months after the last SGN-35 dose. In addition, consultation with a hepatologist is recommended.
- 3.3.6** Patients with a known hypersensitivity to any excipient contained in the drug formulation.
- 3.3.7** Patients with dementia or an altered mental state that would preclude the understanding and rendering of informed consent.
- 3.3.8** Patients with a prior history of documented pancreatitis.
- 3.3.9** Patients with severe renal impairment (CrCL <30 mL/min). A calculated CrCl is acceptable.

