4.1 Access to the Registration Program

Prior to registration, eligibility criteria must be confirmed by the assigned QAM. The study coordinator will screen all subjects for potential registration via the web-based application NOTIS (Northwestern Oncology Trial Information System), which is available at: <https://notis.nubic.northwestern.edu>. Please note that a username and password is required to use this program, and will be provided during site activation prior to training on the NOTIS system.

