5.2.2 Dose and Administration

Study treatment must not be administered as an IV push or bolus.

Study treatment will be administered by outpatient IV infusion given over approximately 30 minutes on Day 1 of each 21-day cycle. For this “lead in” phase, there are a total of 2 cycles. In the absence of infusion toxicities, the infusion rate for all patients must be calculated in order to achieve a 30-minute infusion period. Study treatment will be administered through a dedicated IV line and cannot be mixed with other medications.

The dose of SGN-35 for lead-in is: **1.8 mg/kg**. Dosing is based on patient weight according to the institutional standard; however, doses will be adjusted for patients who experience a $\geq 10\%$ change in weight from baseline. Actual weight will be used except for patients weighing greater than 100 kg; dose will be calculated based on 100 kg for these individuals. The dose will be rounded to the nearest whole number of milligrams.

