• Hematologic	
 Continue at same dose level. 	
 Continue at same dose level. 	
 Withhold dose until toxicity is \leq Grade 2, or has returned to baseline, then resume treatment at the same dose level.^b Consider growth factor support (eg, G-CSF) for treatment of neutropenia and prophylaxis in subsequent cycles. 	
 Withhold dose until toxicity is \leq Grade 2, then resume treatment at the same dose level. Consider growth factor support (eg, G-CSF) for treatment of neutropenia and prophylaxis in subsequent cycles. For the second occurrence of Grade 4 toxicity (if neutropenia, while receiving growth factor support), withhold dose until toxicity is \leq Grade 2, then reduce the dose to 1.2 mg/kg (or to 0.8 mg/kg if already on 1.2 mg/kg) and resume treatment^b

^a Patients who develop Grade 3 or 4 electrolyte laboratory abnormalities or nausea/vomiting that respond to treatment may continue study treatment without interruption.

^b Patients who develop Grade 3 or 4 lymphopenia may continue study treatment without interruption.

^c See Section 5.2.5.1 above regarding specific modifications for pancreatitis.

5.2.6 Treatment Compliance.

Subject compliance with treatment is anticipated to be well controlled for this trial as study treatment will be administered at the study site by the investigator or investigator designee. Treatment administration data will be captured and reviewed to ensure site compliance with the treatment regimen.

5.2.7 Other directions.

See **Section 8.1** for Preparation, Packaging and Labeling, and Concomitant Therapy and other information regarding SGN35.

5.2.8 Re-staging.

The first 22 evaluable patients entered onto the trial will have an “early” FDG-PET scan performed after the 2 ‘lead in’ cycles of SGN35. The recommended timing for this FDG-PET scan is to be completed between days 14 and 18 after the 2nd cycle of SGN35. See **Section 6.6** for further details regarding completion and interpretation of FDG-PET and see Table 3 Schedule of Activities in Section 7.0 for additional details.

5.2.8.1 Re-staging for evaluable patients 23 through 45.

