8.1.6.2 Dilution

Calculate the required volume of 5 mg/mL reconstituted brentuximab vedotin solution needed and withdraw this amount from the vials. The dose for patients with a weight of >100 kg should be calculated for 100 kg. Immediately add the reconstituted solution to an infusion bag containing a minimum volume of 100 mL to achieve a final concentration of 0.4 mg/mL to 1.8 mg/mL brentuximab vedotin. Brentuximab vedotin can be diluted into 0.9% Sodium Chloride Injection, 5% Dextrose Injection or Lactated Ringer's Injection. Gently invert the bag to mix the solution. Brentuximab vedotin contains no bacteriostatic preservatives. Following dilution, infuse the brentuximab vedotin solution immediately, or store the solution at 2-8°C (36-46°F) and use within 24 hours of reconstitution. DO NOT FREEZE.

8.1.7 **Administration. Study treatment must not be administered as an IV push or bolus.** Study treatment will be administered by outpatient IV

infusion given over approximately 30 minutes on Day 1 of each 21-day cycle. For this “lead in” phase, there are a total of 2 doses/cycles. In the absence of infusion toxicities, the infusion rate for all patients must be calculated in order to achieve a 30-minute infusion period. Study treatment will be administered through a dedicated IV line and cannot be mixed with other medications.

- **Avoid use in patients with severe renal impairment**
- **Avoid use in patients with moderate or severe hepatic impairment.**

Required Premedication and Postmedication. Routine premedication is not mandated prior to the first dose of study treatment. However, patients at clinical risk of nausea or who experience a Grade 1 or Grade 2 infusion-related reaction may receive subsequent study treatment with premedication as described below (e.g., prochlorperazine, ondansetron, etc).

8.1.8 **Incompatibilities.** No other anti-cancer treatment will be permitted during the treatment period, including chemotherapy, investigational therapies, radiation, biological response modifiers, hormone therapy, or immunotherapy.

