Also Reported on SGN-35 Trials But With the Relationship to SGN-35 Still Undetermined: Acute kidney injury; Adult respiratory distress syndrome; Alanine aminotransferase increased; Aspartate aminotransferase increased; Dehydration; Encephalopathy; Generalized muscle weakness; Hot flashes; Hyperkalemia; Hypertension; Hypocalcemia; Hypophosphatemia; Hypotension; Infections and infestations - Other (oral candidiasis); Investigations - Other (blood LDH increased); Lymphocyte count decreased; Meningitis; Myelodysplastic syndrome; Myositis; Neck pain; Non-cardiac chest pain; Pericardial effusion; Pharyngitis; Pleural effusion; Pneumothorax; Productive cough; Renal and urinary disorders - Other (Pyelonephritis); Reproductive system and breast disorders - Other (groin pain); Respiratory, thoracic and mediastinal disorders - Other (oropharyngeal pain); Sinus tachycardia; Sinusitis; Skin infection; Syncope; Urinary tract infection

Please refer to current Investigator's brochure for detailed information on all side effects.

- 8.1.12 **Nursing/patient implications.** Please see above under administration in Section 8.1.7. In addition, avoid the use of SGN35 in patients with moderate (Child-Pugh B) or severe (Child –Pugh C) hepatic impairment. Regarding management of infusion reactions, infusion-related reactions

may occur during the infusion of study treatment. The infusion is to be administered at a site properly equipped and staffed to manage anaphylaxis should it occur. The patient should be observed for at least 60 minutes following the first infusion of study treatment. During this observation period, the IV line should remain open for at least 1 hour to allow administration of IV drugs if necessary. All supportive measures consistent with optimal patient care will be given throughout the study according to institutional standards. This includes adjusting the infusion time if necessary. Medications for infusion-related reactions, such as epinephrine, antihistamines, and corticosteroids, should be available for immediate use.

Patients who experience a Grade 1 or Grade 2 infusion-related reaction may receive subsequent study treatment infusions with premedication consisting of acetaminophen (650 mg orally) and diphenhydramine (25–50 mg orally or 10–25 mg IV) or according to institutional standards, administered 30–60 minutes prior to each 30-minute infusion.

8.2 Doxorubicin.

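### The protocol says to avoid SGN-35 in Child-Pugh B or C hepatic impairment, but only the companion renal limit was made an eligibility criterion

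*Combined protocol and SAP*

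**What the plan says.** Section 8.1.7 (Administration of SGN-35) lists two warnings next to each other. One concerns severe renal impairment. The other reads "Avoid use in patients with moderate or severe hepatic impairment". Section 8.1.12 repeats the second and defines its lower grade: "avoid the use of SGN35 in patients with moderate (Child-Pugh B) or severe", with Child-Pugh C given for the severe grade.

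In Section 3 the renal warning has a matching exclusion, 3.3.9: "Patients with severe renal impairment (CrCL <30 mL/min). A calculated CrCl is acceptable". For the liver, inclusion 3.1.9 sets "creatinine < 2.5 mg/dl, and bilirubin < 3.0 mg/dl", within a list that begins "Adequate organ function including an ANC". Exclusion 3.3.5 deals with hepatitis B only.

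Section 4.1 makes the Section 3 criteria the test for entry: "Prior to registration, eligibility criteria must be confirmed by the assigned QAM". Treatment then opens with two doses of SGN-35 at 1.8 mg/kg (5.1 and 5.2.2). Section 5.2.7 refers sites to Section 8.1 "for Preparation, Packaging and Labeling, and Concomitant Therapy and other information regarding SGN35".

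**The concern.** The two warnings stand together in 8.1.7, but only one reached the list that is checked before registration. A patient with moderate or severe hepatic impairment and bilirubin under 3.0 mg/dl can meet every listed criterion, be registered, and be scheduled for a drug that Section 8.1 says to avoid. What is at stake is the safety of an individual patient aged 60 or over. The warning should be caught at the central check but depends on someone applying Section 8.1 at the first infusion.

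**Working it through.** No power or error-rate figure is involved. The check sets each limit in 8.1.7 against the whole of Section 3, then follows the patient from registration to dose 1.

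**Step 1. Match limits to criteria.** Section 3 has 12 inclusion items (3.1.1 to 3.1.12) and 9 exclusion items (3.3.1 to 3.3.9), so 12 + 9 = 21 in all.

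| Limit on SGN-35 | Where stated | Related laboratory limit in 3.1.9 | Matching exclusion |
|---|---|---|---|
| Severe renal impairment | 8.1.7 | Creatinine < 2.5 mg/dl | 3.3.9 (CrCl < 30 mL/min) |
| Moderate or severe hepatic impairment | 8.1.7, 8.1.12 (Child-Pugh B/C) | Bilirubin < 3.0 mg/dl | None |

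Of the two limits, one is carried into Section 3. None of the 21 criteria names hepatic impairment or a Child-Pugh class.

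**Step 2. Ask whether another criterion does the same work.**

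- *Bilirubin (3.1.9).* This is a threshold on one analyte, while 8.1.12 defines its limit by class. The plan itself treats some of the admitted range as abnormal: under the heading of hepatic dysfunction, 5.3.3.2 halves vinblastine and doxorubicin when bilirubin is above 1.5 and below 3.0, and 3.1.9 admits all of that range. This does not make such patients Child-Pugh B. It shows only that the ceiling was not set to exclude liver dysfunction. The table in 5.3.3.2 has no SGN-35 rule.
- *Renal parallel.* 3.1.9 also contains a creatinine ceiling, and the plan still carries 3.3.9. A single-analyte ceiling was not relied on for the kidney.
- *Hepatitis B (3.3.5).* This excludes known HBsAg-positive infection. Other causes of liver impairment are outside it.
- *Mental state (3.3.7).* This applies only where understanding and consent are precluded.

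**Step 3. See what the registration check covers.** Under 4.2.1 the site submits the eligibility eCRF, the signed consent, the pathology report and a checklist signed by the treating physician. The check in 4.1 is against the eligibility criteria. As no criterion mentions the hepatic limit, nothing in the protocol text directs that check to it.

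**Step 4. Follow the registered patient to dose 1.** "The dose of SGN-35 for lead-in is" 1.8 mg/kg. Section 5.1 describes no route that omits the lead-in. Table 3 governs toxicity after treatment has begun, not impairment present at entry. The remaining safeguard is 5.2.7, which leads to 8.1 and so to 8.1.7 and 8.1.12.

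**Step 5. Look for a stated reason.** The history of changes (Amendment 8) records 3.3.9 and both 8.1.7 warnings as added on the same ground, updated prescribing information. It gives no reason for treating the two differently. This agrees with the current text and is cited only as background; the gap lies in the current text.

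**The case against.** The strongest reply is that the protocol already bars the harm. Sections 8.1.7 and 8.1.12 are operative text, 5.2.7 sends sites there, and 11.6 requires conduct exactly as the protocol describes, so dosing such a patient would be a departure from it. The open wording of 3.1.9 lets an investigator decline the patient. The treating physician signs the checklist with pre-study chemistries, abdominal CT and a comorbidity rating scheduled in Table 4. The checklist and eligibility eCRF are not reproduced, so what sites actually screen cannot be fully seen.

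Most of this stands. Section 3 is silent rather than contradictory, and the gap does not license dosing. It does not answer the narrower point: the hepatic warning takes effect only after registration and relies on discretion, while its renal twin is a fixed criterion confirmed centrally.

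A reader might infer more than the documents support:

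- *That consolidation is unguarded.* Section 5.4.1 refers back to 5.2, which includes 5.2.7 and so leads to 8.1; 8.1.5.2 also covers consolidation dosing.
- *That the CIRS liver item arrives too late.* Table 4 schedules the comorbidity assessment pre-study. The five days after registration in Appendix VIII are for submitting the form.
- *That the class cannot be derived from the scheduled tests, or that a particular range of Child-Pugh scores passes 3.1.9.* The documents do not reproduce the scoring, so neither claim can be settled from them.
- *That a patient admitted this way would receive every planned SGN-35 dose.* That would require a standing instruction to be missed again and again.

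**Conclusion.** The point holds as an inconsistency between eligibility and the drug section. A limit stated twice in Section 8.1 has no counterpart in Section 3, while the limit beside it does. The central check therefore does not screen for a condition in which the protocol says to avoid the opening drug.

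Its size is modest. The wording is to avoid, which is softer than a prohibition, and the warning still applies at dosing. The documents give no frequency of Child-Pugh B or C in this population and none is assumed; the number affected is probably small. A reader might go on to infer a loss of evaluable patients, because 9.2.2 requires both lead-in doses, but without a frequency there is no basis for that. No effect on power, on the stage 1 decision or on the CR analysis is claimed.

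The conclusion rests on the protocol text alone and assumes that the unseen checklist and eCRF follow Section 3. If they already ask about hepatic impairment, the change only brings Section 3 into line with practice.

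**What to change.** Add exclusion 3.3.10: *Moderate (Child-Pugh B) or severe (Child-Pugh C) hepatic impairment.*

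For patients with known or suspected liver disease, record the Child-Pugh class before the eligibility checklist is signed, using routine bloods as needed. Suspicion can come from the pre-study CIRS liver item, baseline imaging or abnormal liver tests. Other patients need nothing further. Undiagnosed disease that none of these flags would still be missed, so 8.1.7 and 8.1.12 should stay as they are.

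This is a cheap improvement: one line in Section 3, one note in the pre-study schedule, and routine blood tests in a subset of patients. The downside is that a few patients with liver impairment, including some whose impairment is due to lymphoma, are excluded. For them 8.1.7 already says to avoid SGN-35, and the protocol offers no treatment path without it.

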4 PATIENT REGISTRATION

NOTE: Patients *may not* begin protocol treatment prior to registration. All patient registrations will be registered centrally through the Clinical Research Office at Northwestern University before enrollment to study. Please contact the assigned Quality Assurance Monitor (QAM) or email the QA Department ([contact]) for questions regarding patient registration.

4.1 Access to the Registration Program

Prior to registration, eligibility criteria must be confirmed by the assigned QAM. The study coordinator will screen all subjects for potential registration via the web-based application NOTIS (Northwestern Oncology Trial Information System), which is available at: <https://notis.nubic.northwestern.edu>. Please note that a username and password is required to use this program, and will be provided during site activation prior to training on the NOTIS system.

4.2 Registering a Patient

4.2.1 BEFORE a patient can be treated on study, please complete and submit the following items to confirm eligibility and receive an identification number:
:

4.2.1.1 Eligibility eCRF (complete in NOTIS)

4.2.1.2 Patient's signed and witnessed informed consent form (upload to NOTIS).

4.2.1.3 Copy of pathology report (upload to NOTIS)

4.2.1.4 Eligibility checklist (signed and dated by the treating physician – upload to NOTIS)

[figure not shown]
4.2.2 Training on eCRF completion will be provided at the time of site activation. Please refer to the eCRF demonstration videos on the CRO website for additional instructions on registering a patient. The QAM will review the registration, register the patient, assign a subject identification number, and send a confirmation of registration to study personnel. Registration will then be complete and the patient may begin study treatment.

5 TREATMENT PLAN

5.1 Overall description.

Therapy on this protocol is divided into 3 phases: 1) SGN-35 “lead in” as a single-agent for 2 cycles/doses (1.8 mg/kg q 3 weeks x 2 doses); 2) AVD chemotherapy for 6 cycles; and 3) SGN-35 consolidation with SGN-35 given as a single-agent once every 3 weeks for 4 total doses (see Figure 2).

Figure 2. Trial schema.

* Any patient who has not achieved a CR or PR after 6 cycles of AVD should be taken off study and not proceed with SGN35 consolidation therapy; however patients who do not complete 6 cycles of AVD (due to toxicity: designated ‘chemotherapy intolerant’), but have achieved PR or CR may proceed with SGN35 consolidation therapy.

5.2 SGN-35 “lead in”.

5.2.1 SGN-35 Description

SGN-35 (brentuximab vedotin) is an antibody-drug conjugate consisting of the anti-CD30 antibody cAC10 conjugated to MMAE, an anti-tubulin agent.

5.2.2 Dose and Administration

Study treatment must not be administered as an IV push or bolus.

Study treatment will be administered by outpatient IV infusion given over approximately 30 minutes on Day 1 of each 21-day cycle. For this “lead in” phase, there are a total of 2 cycles. In the absence of infusion toxicities, the infusion rate for all patients must be calculated in order to achieve a 30-minute infusion period. Study treatment will be administered through a dedicated IV line and cannot be mixed with other medications.

The dose of SGN-35 for lead-in is: **1.8 mg/kg**. Dosing is based on patient weight according to the institutional standard; however, doses will be adjusted for patients who experience a $\geq 10\%$ change in weight from baseline. Actual weight will be used except for patients weighing greater than 100 kg; dose will be calculated based on 100 kg for these individuals. The dose will be rounded to the nearest whole number of milligrams.

5.2.3 Required Premedication and Postmedication

Routine premedication should not be administered prior to the first dose of study treatment. However, patients who experience a Grade 1 or Grade 2 infusion-related reaction may receive subsequent study treatment with premedication as described immediately below.

